#### **10.4 Criteria for Subject Selection (In- and Exclusion)**

Following receipt of verbal and written information about the trial, the parent(s) or legal guardian(s) or the subject (as appropriate and according to national laws or regulations) must provide **signed and dated informed consent** before any trial related activity is carried out, including activities relating to washout periods.

Any implementation of national requirements/law for the trial subject’s participation in the clinical trial will be ensured and will be described in submission documentation to authorities/ethics committees, as applicable.

## 10.4.1 Inclusion Criteria

### 10.4.1.1 Inclusion Criteria for *All* Subjects

1. Signed informed consent given by parent(s), or legal guardian(s), or by the subject (according to national law) following their receipt of verbal and written information about the trial.
2. Subjects will receive verbal and written information and will provide written assent to the trial.
3. Subjects 12 to 16 years, 11 months of age.
4. Either sex.
5. Any race or ethnicity.
6. Clinical signs of psoriasis vulgaris on both the scalp and body (trunk and/or limbs).
7. At SV2 and Visit 1, a clinical diagnosis of scalp and body (trunk and/or limbs) psoriasis which is:
  - a. of an extent of 10 to 35% of the body surface area (excluding psoriatic lesions of the face and sensitive areas. Sensitive areas include armpits, groin, under the breasts and in other skin folds around the genitals and buttocks), and
  - b. of at least moderate severity according to the investigator's global assessment of disease severity on the body, and
  - c. for subjects aged 12 to 14 years with a BSA  $\leq 1.3 \text{ m}^2$ , amenable to topical treatment with a maximum of 50 g of investigational product per week, and
  - d. for subjects aged 12 to 14 years with a BSA  $> 1.3 \text{ m}^2$ , amenable to topical treatment with a maximum of 75 g of investigational product per week, and
  - e. for subjects aged 15 to 16 years, 11 months with a BSA  $\leq 1.7 \text{ m}^2$ , amenable to topical treatment with a maximum of 75 g of investigational product per week, and
  - f. for subjects aged 15 to 16 years, 11 months with a BSA  $> 1.7 \text{ m}^2$ , amenable to topical treatment with a maximum of 100 g of investigational product per week.
8. A serum albumin-corrected calcium below the upper reference limit at SV2.

9. Females of child-bearing potential must have a negative urine pregnancy test result and must agree to use a highly effective method of contraception during the trial. Highly effective methods are defined as ones which result in a low failure rate (less than 1% per year) such as progestin-only formulations (implants, injectables, or “mini-pill” in combination with a barrier method), some intra-uterine devices, double barrier methods (eg. cervical cap and condom), tubal ligation/section, sexual abstinence or vasectomised partner. The patients must have used the contraceptive method for at least 1 month prior to the pregnancy test, and must continue using the contraceptive method for at least 1 week after the last application of investigational product. A female is defined as not of child-bearing potential if she is premenarchal, postmenopausal or surgically sterile (hysterectomy or bilateral ovariectomy).
10. Subjects fulfilling national requirements/law for participation in this trial.

#### **10.4.1.2 Additional Inclusion Criteria for Subjects Performing HPA Axis Assessments (U.S. only)**

1. At SV2 and Visit 1, a clinical diagnosis of scalp psoriasis which is:
  - a. more than or equal to 20% of the scalp area, and
  - b. of at least moderate severity according to the investigator’s global assessment of disease severity on the scalp.
2. Subjects with a normal HPA axis function at SV2 including serum cortisol concentration above 5 mcg/dl before ACTH challenge and serum cortisol concentration above 18 mcg/dl 30 minutes after ACTH challenge.

#### **10.4.1.3 Additional Inclusion Criteria for Subjects *Not* Performing HPA Axis Assessments**

1. At SV2 and Visit 1, a clinical diagnosis of scalp psoriasis which is:
  - a. more than or equal to 10% of the scalp area, and
  - b. of at least moderate severity according to the investigator’s global assessment of disease severity on the scalp.

### **10.4.2 Exclusion Criteria**

#### **10.4.2.1 Exclusion Criteria for *All* Subjects**

1. A history of hypersensitivity to any component of the LEO 80185 gel
2. Systemic treatment with biological therapies (marketed or not marketed), with a possible effect on scalp and/or body psoriasis within the following time period prior to Visit 1 and during the trial:
  - a. etanercept – within 4 weeks prior to Visit 1

- b. adalimumab, infliximab – within 2 months prior to Visit 1
  - c. ustekinumab – within 4 months prior to Visit 1
  - d. experimental products – within 4 weeks/5 half-lives (whichever is longer) prior to Visit 1
3. Systemic treatment with therapies other than biologicals, with a possible effect on scalp and/or body psoriasis (e.g., retinoids, immunosuppressants, PUVA) within 4 weeks prior to Visit 1 (Day 0) or during the trial.
  4. UVB therapy within 2 weeks prior to Visit 1 or during the trial.
  5. Any topical treatment on the scalp and body (except for emollients and non-steroid medicated shampoos) within 2 weeks prior to Visit 1 or during the trial.
  6. Systemic calcium, vitamin D supplements, antacids, diuretics, antiepileptics, diphosphonates or calcitonin within 4 weeks prior to SV2 or during the trial.
  7. Planned initiation of, or changes to, concomitant medication that could affect psoriasis (e.g., betablockers, chloroquine, lithium, ACE inhibitors) during the trial.
  8. Current diagnosis of guttate, erythrodermic, exfoliative or pustular psoriasis.
  9. Subjects with any of the following conditions present on the treatment areas on scalp and/or body: viral (e.g., herpes or varicella) lesions of the skin, fungal and bacterial skin infections, parasitic infections, skin manifestations in relation to syphilis or tuberculosis, rosacea, acne vulgaris, acne rosacea, atrophic skin, striae atrophicae, fragility of skin veins, ichthyosis, ulcers and wounds.
  10. Other inflammatory skin diseases that may confound the evaluation of scalp and/or body psoriasis.
  11. Planned excessive exposure to sun during the trial that may affect scalp and/or body psoriasis.
  12. Known or suspected severe renal insufficiency or severe hepatic disorders.
  13. Known or suspected disorders of calcium metabolism associated with hypercalcaemia.
  14. Any clinically significant abnormality following review of screening laboratory tests (blood and urine samples), physical examination or blood pressure/heart rate measurement performed at SV2.
  15. Current participation in any other interventional clinical trial.
  16. Previously enrolled in this trial.
  17. Subjects who have received treatment with any non-marketed drug substance (i.e., an agent which has not yet been made available for clinical use following registration) within a month prior to SV1 or longer, if the class of substance required a longer wash-out as defined above (e.g., biological treatments).
  18. Subjects or parent(s) or legal guardian known or suspected of being unlikely to comply with the Clinical Trial Protocol (e.g., alcoholism, drug dependency or psychotic state).

19. Females who are pregnant, or of child-bearing potential and wishing to become pregnant during the trial, or who are breast-feeding.
20. Females of child-bearing potential with positive pregnancy test at SV2.
21. Subject (or their partner) not using an adequate method of contraception according to national requirements.

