#### Washout/Screening Period

Depending on the prior use of disallowed treatments, the washout/screening period will last for 7 to 56 days prior to the first administration of LEO 80185 gel (Visit 1).

Prior to attending any study procedure, a signed informed consent must be obtained from the parent(s)/legal guardian(s) of the subject, or by the subject (as appropriate and according to national laws and regulations). Written assent should also be obtained from the subject. There are two screening visits: Screening visit 1 (SV1) and screening Visit 2 (SV2). Depending on the subjects' use of excluded treatments, SV1 is performed up to 7 weeks before SV2; SV2 is performed at 3 to 7 days before Visit 1.

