#### **10.6.10 Prior and Concomitant Treatment**

Use of concomitant treatment should be recorded in the subject's medical record and the CRF (treatment/drug name, dose, indication and dates of start and stop).

Use of non-marketed/other investigational products one month prior to SV1 and during the trial is not permitted.

Changes of doses (including starting) of drugs that, while not specifically indicated for treatment of the indication being studied, are known to have an effect (positive or negative) on the indication, are not permitted.

For all subjects, treatments requiring washout before SV2/Visit 1 are listed below, with the required individual washout periods indicated in brackets:

- Topical treatment with corticosteroids (2 weeks prior to SV2)
- Systemic treatment with biological therapies (marketed or not marketed), with a possible effect on scalp or body psoriasis (etanercept) (4 weeks prior to Visit 1), adalimumab, infliximab (2 months prior to Visit 1)\*, ustekinumab (4 months prior to Visit 1)\* or experimental products (4 weeks/5 half-lives (whichever is longer) prior to Visit 1)
- Systemic treatment with therapies other than biologicals, with a possible effect on scalp or body psoriasis (e.g., retinoids, immunosuppressants, PUVA) within 4 weeks prior to Visit 1
- UVB therapy within 2 weeks prior to Visit 1
- Any topical treatment on the scalp or body (except for emollients and non-steroid medicated shampoos) within 2 weeks prior to Visit 1
- Systemic calcium, vitamin D supplements, antacids, diuretics, antiepileptics, diphosphonates or calcitonin (4 weeks prior to SV2)

*\* Note: the time between SV1 and Visit 1 cannot be longer than 8 weeks, and between SV1 and SV2 not longer than 7 weeks, therefore subjects receiving, or having recently received, these treatments at SV1 cannot be enrolled.*

For subjects performing HPA axis assessments, additional treatments requiring washout before SV2/Visit 1 are listed below, with the required individual washout periods indicated in brackets:

- Systemic treatment with corticosteroids (including inhaled and nasal steroids) (12 weeks prior to SV2)\*
- Oestrogen therapy (including contraceptives) or any other medication known to affect cortisol levels or HPA axis integrity (4 weeks prior to SV2)

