- Enzymatic inductors (e.g., barbiturates, phenytoin, rifampicin), systemic or topical cytochrome P450 inhibitors (e.g., ketoconazole, itraconazole, metronidazole), hypoglycaemic sulfonamides, antidepressive medications (4 weeks prior to SV2). Topical ketoconazole (2 weeks prior to SV2).

Treatments which cannot be used during the treatment period (Visits 1-5) are the same as those requiring a washout period, as listed previously, with the addition that the following are not allowed:

- Initiation of, or changes to, concomitant medication that could affect scalp or body psoriasis (e.g. beta-blockers, lithium, anti-malaria drugs, ACE inhibitors).
- Excessive exposure of treated areas to either natural or artificial sunlight (including tanning booths, sunlamps, etc.).

The following concomitant anti-psoriatic treatments are allowed during the trial:

Scalp: No other treatment allowed. Non-medicated shampoo is allowed.

Trunk/limbs: No other treatment allowed. Bath oils and moisturizing soaps are allowed.

Face and sensitive areas: For subjects performing HPA axis assessments: Any topical treatment allowed except corticosteroids. Bath oils and moisturizing soaps are allowed. For subjects *not* performing HPA axis assessments: Any topical treatment allowed except potent or very potent (WHO groups III-IV) corticosteroids. Bath oils and moisturizing soaps are allowed.

Sensitive areas refers to armpits, groin, under the breasts and in other skin folds around the genitals and buttocks.

The maximum amount of topical treatment containing vitamin D analogues (calcipotriol, calcitriol or tacalcitol) is limited to the following including the amount of investigational product used:

- 50 g ointment/gel/cream per week for subjects aged 12 to 14 years with a BSA  $\leq 1.3 \text{ m}^2$ .
- 75 g ointment/gel/cream per week for subjects aged 12 to 14 years with a BSA  $> 1.3 \text{ m}^2$  and subjects aged 15 to 16 years, 11 months with a BSA  $\leq 1.7 \text{ m}^2$ .
- 100 g ointment/gel/cream per week for subjects aged 15 to 16 years, 11 months with a BSA  $> 1.7 \text{ m}^2$ .

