## **10.9 Safety Evaluation**

### **10.9.1 Primary Response Criteria**

- Adverse drug reactions (ADRs)
- Subjects with serum cortisol concentration of  $\leq 18$  mcg/dl at 30 minutes after ACTH-challenge at Week 4 and at Week 8
- Change in albumin-corrected serum calcium from baseline (SV2) to Week 4, Week 8, and end of treatment
- Change in 24-hour urinary calcium excretion from baseline (SV2) to Week 4, Week 8, and end of treatment

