6.3 Analysis of Safety

The analysis of safety will be based on the safety analysis set according to the defined response criteria in the protocol, with the exception of the ACTH-challenge test which will be based on the per protocol analysis set.

Baseline for the safety analysis is defined as last observation collected prior the first application of IMP, which is Screening Visit 2.

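### The two-week wash-out for topical vitamin D analogues on scalp and body is counted from Visit 1, although the primary calcium baseline is taken at SV2, 3 to 7 days earlier

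*Protocol*

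**What the plan says.** **Baseline.** Protocol 10.9.1 lists two calcium measures among the primary response criteria: "Change in albumin-corrected serum calcium from baseline (SV2) to Week 4, Week 8, and end of treatment" and "Change in 24-hour urinary calcium excretion from baseline (SV2) to Week 4, Week 8, and end of treatment". SAP 6.3 agrees: "Baseline for the safety analysis is defined as last observation collected prior the first application of IMP, which is Screening Visit 2". Protocol 10.1 fixes the visit: "SV2 is performed at 3 to 7 days before Visit 1". Protocol 10.8.4.1 lets the 24-hour urine be collected up to three days before the visit. The schedule in Protocol 3.1 has no calcium sample at Visit 1.

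**Wash-outs counted from Visit 1.** Exclusion criterion 5 in Protocol 10.4.2.1 excludes "Any topical treatment on the scalp and body (except for emollients and non-steroid medicated shampoos) within 2 weeks prior to Visit 1", and Protocol 10.6.10 repeats it as "Any topical treatment on the scalp or body (except for emollients and non-steroid medicated shampoos) within 2 weeks prior to Visit 1".

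**Wash-outs counted from SV2.** Criterion 6 covers systemic calcium, vitamin D supplements and other agents that act on calcium, ending with "diphosphonates or calcitonin within 4 weeks prior to SV2 or during the trial". Protocol 10.6.10 also counts topical corticosteroids from SV2, two weeks before it, in its list for all subjects.

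**Face and sensitive areas.** Protocol 10.6.10 allows topical treatment there, apart from corticosteroids (HPA subjects) or potent and very potent corticosteroids (other subjects). It sets a weekly ceiling: "The maximum amount of topical treatment containing vitamin D analogues (calcipotriol, calcitriol or tacalcitol) is limited to the following including the amount of investigational product". The ceilings are 50, 75 or 100 g by age and BSA. The Synopsis (Methodology) and Protocol 5.3 are narrower for HPA subjects: only non-steroid topicals from which no systemic effect is expected.

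**Stated intent.** Protocol 8.3 says that treatments able to affect calcium metabolism will be washed out, and names vitamin D among the examples without giving a route.

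**The concern.** Calcipotriol is a vitamin D analogue, and Protocol 8.3 explains that absorbed topical calcipotriol acts on calcium metabolism for that reason. A subject who used calcipotriol alone on scalp and body shortly before screening has had the same class of exposure that the trial sets out to measure.

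Elsewhere the plan counts a wash-out from SV2 when the treatment could disturb an SV2 test. Systemic calcium-related drugs are counted that way for the calcium tests, and corticosteroids for the ACTH test. Topical vitamin D monotherapy is the exception. It appears to be handled only as an anti-psoriatic treatment, for which Visit 1 is a natural reference point.

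The trial has one arm, so change from SV2 is the only contrast for these two criteria. A residual effect at SV2 makes the change look smaller, which is the unsafe direction when the question is whether the gel disturbs calcium. Analogue use on face or folds that starts after SV2 acts the other way. The SAP text and the calcium tables in its Appendix I do not take account of concomitant vitamin D analogues.

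**Working it through.** The plan gives no figure of its own for this point, so the check is calendar arithmetic.

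**Inputs**
- Last permitted scalp or body use under criterion 5: Day -14 (two weeks before Visit 1, Day 0).
- SV2: Day -7 to Day -3 (Protocol 10.1 and 3.1).
- Baseline urine: 0 to 3 days before SV2 (Protocol 10.8.4.1).
- Systemic calcium and vitamin D: 4 weeks before SV2 (criterion 6).
- Longest SV1 to SV2 interval: 7 weeks; SV1 to Visit 1: 8 weeks (Protocol 10.6.10).

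**Step 1: interval before baseline blood** = SV2 day + 14.
- SV2 on Day -7: -7 + 14 = 7 days.
- SV2 on Day -3: -3 + 14 = 11 days.

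**Step 2: interval before baseline urine** = SV2 day + 14, less 0 to 3 days.
- SV2 on Day -7: 4 to 7 days.
- SV2 on Day -3: 8 to 11 days.
- Overall: 4 to 11 days. The 4-day end needs last use on Day -14, SV2 on Day -7 and the earliest urine collection together.

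**Step 3: comparison.** Systemic supplements stop at least 28 days before SV2, and topical corticosteroids under 10.6.10 at least 14. For face and folds no wash-out from vitamin D analogues is stated, so the minimum interval is 0 days and use can be ongoing at baseline.

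**Step 4: the same two weeks counted from SV2.** Last use moves to Day -7 - 14 = -21 or Day -3 - 14 = -17, which is 7 or 3 days earlier than Day -14. The interval is then at least 14 days before blood and 14 - 3 = 11 days before the earliest urine. Fourteen days fits within the 49 days allowed between SV1 and SV2, and the existing 28-day systemic wash-out already has to fit there.

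**Step 5: possible effect on the mean change (assumed values, not from the documents).** Let a share f of subjects still carry a fraction r of the on-treatment effect at SV2, with the same true effect in everyone. Then observed change / true change = 1 - f × r.

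| f | r | observed / true |
|---|---|---|
| 0.10 | 0.25 | 1 - 0.025 = 0.975 |
| 0.25 | 0.50 | 1 - 0.125 = 0.875 |
| 0.50 | 1.00 | 1 - 0.50 = 0.50 |

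The range runs from negligible to halved, and the documents do not place the trial within it. If there is no carry-over, r is 0 for past users and only ongoing face or fold use counts.

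**The case against.** The case on the other side is substantial, and most of it limits the point without removing it.

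- **No bias is shown.** Scalp and body users are 7 to 11 days off the analogue at the blood sample. The documents give no evidence that an effect lasts that long. Protocol 8.3 reports no significant effect on calcium at recommended amounts, and serum calcium within the normal range at up to 300 g. This stands: the size may be small. It does not settle the matter, because the effect in adolescents is what the trial is meant to measure.
- **Detection of hypercalcaemia does not depend on the change.** Protocol 10.11.5.5 provides absolute values, shift tables and listings of out-of-range values, and inclusion criterion 8 requires calcium below the upper limit at SV2. This stands. These safeguards do not correct a shift within the normal range, which is where a mean change would show it.
- **Combination products are covered.** A product that pairs an analogue with a corticosteroid falls under the SV2-based corticosteroid rule in 10.6.10. The gap is therefore mainly one for monotherapy. The exclusion criteria give that rule only for HPA subjects (10.4.2.2), so the sections disagree about everyone else.
- **Face and fold use is not free for all.** The Synopsis and Protocol 5.3 may bar analogues there for HPA subjects. Protocol 10.6.10 does not repeat the limit, so this is a conflict to resolve.
- **Protocol 8.3 may mean only systemic vitamin D.** Its calcium examples track criterion 6, and it mentions topical anti-psoriatic therapy separately. It shows an intent, and is not clear proof of a broken rule.
- **The data can help.** Drug name, dose, indication and start and stop dates are recorded (10.6.10) and listed (SAP Listing 4-6), so users can be identified. A reader might infer that the two effects can never be told apart. That goes too far.

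A reader might also infer that analogues should be washed out at every site. The documents do not support that. No face or fold wash-out exists to be moved. Protocol 10.6.10 makes the treatments barred during Visits 1 to 5 the same as those needing a wash-out, so listing face and fold analogues there would forbid use that the same section permits. Washing users out for SV2 and letting them resume would build in the inflated change described above.

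**Conclusion.** The point holds as a mismatch of reference visits. For topical vitamin D analogues used alone on scalp and body, the wash-out is counted from Visit 1 while the primary calcium baseline is SV2. The guaranteed interval is 7 to 11 days before blood and 4 to 11 days before urine, against 28 days for systemic supplements. Face and fold use adds a second route, with no minimum interval and with sections that do not agree.

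The likely direction is a mean change drawn towards no effect, or an inflated one where face or fold use begins after SV2. The size is unknown and may be small. It depends on the share of users and on carry-over, and the documents give neither. A reader might infer that the baseline was in fact contaminated, or that the trial would miss hypercalcaemia. The documents support neither inference: the first needs those two unknowns, and the second rests on absolute values that the baseline does not touch. This is an inexpensive improvement to two primary criteria, not a flaw that invalidates them.

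The conclusion rests on the supplied protocol text and on reading body in criterion 5 as trunk and limbs, as elsewhere in the protocol. Reading the folds into it would contradict 10.6.10, because criterion 5 also applies during the trial. The SAP cites protocol versions 4.0 and 6.0. Its Table 1 shows no change to this wash-out, but lists only amendments that bear on statistical reporting, so the later versions should be checked.

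**What to change.** 1. **Reference visit.** In 10.4.2.1 and 10.6.10, count the existing two-week scalp and body interval back from SV2 for topical vitamin D analogues, as the plan's other test-related wash-outs are counted. Cost: 3 to 7 more wash-out days for the subjects concerned, within the present screening window.
2. **Sensitivity summary.** From the concomitant medication record, flag subjects with any analogue use overlapping SV2 or shortly before it (the plan's own two weeks before the baseline sample is a workable definition), and separately those with non-study analogue use during treatment. Present SAP Tables 3-5 and 3-8 with and without the flagged subjects, and state how many there are. Cost: one flag and two repeated tables, with no new data. Two limits apply. The protocol defines concomitant medication as medication taken during the trial, so a subject who stopped before SV1 may be missed. SAP section 5 says that the SAP was written after review of the data, so the summary should be labelled as added at that stage. For data already collected, this is the only one of the two measures that can still act.
3. **Reconciliation.** Bring the Synopsis (Methodology), Protocol 5.3, 8.3, 10.4.2.1, 10.4.2.2 and 10.6.10 into agreement on vitamin D analogues on face and folds, and on whom the SV2-based corticosteroid wash-out covers. Which clinical rule should apply is for the sponsor. This point asks for no new face or fold wash-out and no ban.
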